1.1. Prognosis

Most prognostic factors in MF include type and extent of skin involvement and presence or absence of extracutaneous disease, which determine clinical stage (Appendix: Table 1). Recent findings suggest that patient's life expectancy is not adversely affected in stage I A (limited patch, papules and/or plaques covering <10% of the skin surface), while patients diagnosed with tumor disease or erythroderma (stages IIB-IVB) have a worse overall outcome, with median survival of 4 to 5 years [WILLEMZE].

1.2. Aetiology and Pathogenesis

Although the aetiology of MF is unknown, important insights have been gained in the pathogenesis and immunological perturbations that are associated with this disease. Whereas the disease is characterized by infiltration and proliferation of T helper lymphocytes (mainly CD4+) in the skin, CD1a+ Langerhans cells are thought to be involved in its pathogenesis as well. Furthermore there is evidence, that an abnormal cytokine expression in MF might be responsible for tumor progression. Moreover, cytokine loops might explain phenomena like the epidermotropism of malignant cells and/or the depression of the anti-tumor immune response [HWANG].

1.3. Treatment

There is no curative therapy for MF and the aim of treatment is to induce complete remissions of disease and to prolong disease free and finally overall survival while maintaining the patient's quality of life. There have been a large number of uncontrolled studies in MF with response data but virtually no other controlled studies with data on disease free and overall survival. Most comparative studies in MF have been based on relatively small numbers of patients, which has also severely limited any statistical interpretation.

1.3.1. PUVA therapy

It is now commonly accepted that early-stage MF should be initially treated with skin-directed therapies. More aggressive treatments should be reserved for higher stages or progression [TRAUTINGER]. Skin directed therapies include topical corticosteroids, topical chemotherapy, topical bexarotene, radiotherapy and phototherapy. The first report of PUVA treatment [psoralen plus ultraviolet (UV) A] in MF was published in 1976 [GILCHREST]. Since then several groups have successfully used PUVA to treat MF [ROENIGK, HÖNIGSMANN, DIEDEREN]. Today PUVA therapy is a well-accepted first-line treatment option for skin-limited MF, because there is good evidence that it is effective in clearing of skin lesions in early stages of the disease. Long-term remissions can be achieved in a certain percentage of patients [TRAUTINGER]. However, MF lesions may reappear after a very variable time interval with median time to recurrence of 9 to 15 months [WACKERNAGEL].

The mechanism of action of PUVA in MF is not entirely understood. PUVA selectively eliminates T-lymphocyte populations by induction of apoptosis. It causes a functional impairment of CD1a+ Langerhans cells, which are thought to be involved in the pathogenesis of MF by perpetuating the epidermal affinity of infiltrating T cells. It may also act by directly downregulating homing receptors on epidermotropic malignant T cells and by interfering with epidermal cytokine production [HÖNIGSMANN].

1.3.2. Rationale for proposed study

Maintenance PUVA-therapy might be beneficial in slowing relapse of MF after complete initial remission. However, controlled clinical trials concerning PUVA maintenance have not been performed so far [QUERFELD, SANCHEZ, POTHIAWALA]. Moreover, no evidence is available on the optimal frequency and length of maintenance therapy either [HÖNIGSMANN].

2. Objectives of the trial

2.1 General objectives:

To determine whether PUVA maintenance therapy does prolong disease free survival after initial complete response.

3. End-points

3.1. Primary endpoint:

Comparison of median time to recurrence after complete remission between patients treated with maintenance therapy vs. patients without maintenance therapy.

3.2. Secondary endpoints

- Comparison of time from end of treatment to recurrence on condition that the patient is in complete remission at the end of treatment between patients treated with maintenance therapy vs. patients without maintenance therapy.
- Cytokine response in serum and tissue
- Quality of life
- HADS

4. Patient selection criteria

4.1. Inclusion Criteria:

- Histopathologically documented MF clinical stage IA-IIB (see Table1) confirmed by current or previous diagnostic lesion biopsy
- A Karnofsky performance score ≥ 60 (see Table 2)
- Age ≥ 18 years - ≤ 85
- Anti-ds-DNA (antinuclear antibodies) AND anti-Ro/La antibodies: negative
- Acceptable organ function defined as follows:

SGOT (AST) and SGPT (ALT) ≤ 2.5 times the upper limit of normal for the institution

- Creatinine ≤ 2 times the upper limit of normal for the institution
- No evidence of severe cardiac insufficiency (NYHA grade III-IV)
- Women of child bearing potential must have a negative serum or urine pregnancy test (β -HCG) within seven (7) days prior to randomization
- Absence of any serious intercurrent illness or infection at time of entry into the study that could interfere with planned treatment
- Patients must be willing to accept limiting sun exposure on the day receiving PUVA treatment
- Written informed consent

4.2. Exclusion criteria:

- Pregnancy and Lactation
- Photosensitive diseases such as lupus erythematosus or basal cell nevus syndrome
- Skin cancer syndromes such as Xeroderma pigmentosum or basal cell nevus syndrome
- PUVA (oral or topical) treatment within the last 3 months

5. PUVA treatment and follow-up

Psoralens are photosensitising agents. Methoxsalen – the most commonly used drug is a psoralen derivative that is structurally and pharmacologically related to trioxsalen. For PUVA treatment 8-methoxypsoralen (8-MOP) will be used. Patients receive a liquid preparation of 8-MOP (10 mg) in soft gelatine capsules (Oxsoralen®; Gerot Pharmazeutika GmbH, Vienna, Austria, please refer to the Summary of Product Characteristics). The dose of 8-MOP is based on the patient's weight. The standard dose of approximately 10 mg per 20 kg body weight will be given 1 h before UVA exposure, according to the following table:

| Body weight (kg) | 8-MOP (Oxsoralen) dose (10mg = 1 Cps) mg = Cps |
|-------------------------|---|
| < 30 | 10 = 1 |
| 30 - 50 | 20 = 2 |
| 51 - 65 | 30 = 3 |
| 66 - 80 | 40 = 4 |
| 81 - 90 | 50 = 5 |
| 91 - 115 | 60 = 6 |
| > 115 | 70 = 7 |

The initial (starting) UVA dose after psoralen administration will be applied according to the results of skin phototoxicity dose testing. The minimal phototoxic dose (MPD) will be determined by irradiating several skin areas 2 cm in diameter using a Waldmann UVA 800 unit (or similar equipment) with varying light exposure doses and determining the exposure dose that produces slight homogenous erythema at 72 hours. The following dose series will be applied in MPD phototesting: The standard series is Series 1; only if there is no erythema detectable at 72h at any dose in series 1, a second MPD testing with series 2 will be performed and read again at 72h after test exposure:

UVA dose (J/cm²) series

| | | | | | | |
|-----------------|------------|----------|----------|----------|----------|----------|
| Series 1 | 0,5 | 1 | 2 | 3 | 4 | 5 |
| Series 2 | 1,5 | 2 | 3 | 5 | 7 | 9 |

The response in MPD testing will be scored as follows:

Erythema:

-, no erythema; +/- non-homogenous erythema; +, homogenous light erythema; ++, dark erythema; +++, erythema and edema; +++++, blistering

Pigmentation:

-, none; +, slight; ++, moderate; +++, strong; +++++, maximum

The initial dose of UVA administered will be 0.5 (50%) of the MPD. The dose of UVA will be increased weekly by 0-30%, depending on the presence or absence of erythema. Each patient will be treated 2 times a week (treatment week days at least 2 days apart, e.g. Monday/Thursday or Tuesday/Friday). UVA radiation will be delivered using a Waldmann PUVA 7001 K box (Waldmann Medizintechnik, Villingen-Schwenningen, Germany) equipped with Waldmann F85/100 W-PUVA fluorescent bulbs or similar UVA irradiations systems.

Dose adjustments will be done at any treatment, according to the erythema response of the skin:

| | |
|---|---|
| no erythema (-) | regular dose, as scheduled according to protocol (increased by 30% once weekly) |
| non-homogenous erythema (i.e. erythema at certain body sites) (-/+) | same dose, no dose increment |
| homogenous light erythema (+) | skip one exposure and reduce dose to previous dose that was well tolerated |
| dark erythema, edema or blister (++) to +++++) | stop of treatment until remission of skin alterations; reduce dose to previous dose that was well tolerated |

In addition side effects including nausea and vomiting will be recorded on the Initial Therapy sheet and Maintenance Therapy sheet according to the following ratings:

Nausea:

| | |
|---------------|---|
| none (-) | |
| mild (+) | loss of appetite without alteration in eating habits |
| moderate (++) | oral intake decreased without significant weight loss, dehydration or malnutrition |
| severe (+++) | inadequate oral caloric or fluid intake |

Vomiting:

| | |
|---------------|--------------------------|
| none (-) | |
| mild (+) | 1 episode in 24 hours |
| moderate (++) | 2-5 episodes in 24 hours |
| severe (+++) | ≥ 6 episodes in 24 hours |

After 12 weeks of treatment or thereafter at week 16, 20 or 24 (after 24, 32, 40, or 48 PUVA treatments, respectively) patients with complete remission will be randomized by a computer generated list for treatment allocation into two arms (arm A and B, see below). Patients who haven't experienced complete remission after 24 weeks will discontinue active study participation and will enter an observatory study arm.

Patients with complete response will be randomized to receive either PUVA-maintenance therapy (arm A) or no maintenance therapy (arm B) (Figure 1)

Arm A: oral 8-MOP+UVA

Patients will be treated with PUVA maintenance therapy at constant single UVA doses (UVA-dose will be the same as given in the last treatment session in week 12, 16, 20 or 24 of PUVA therapy). Maintenance treatment will be given once a week for one month (4 weeks), every 2 weeks for 2 months (8 weeks) and after three months once a month over 6 months (Appendix: Figure 1). After 9 (10, 11, or 12) months of maintenance therapy (14 treatments) patients will discontinue therapy. If PUVA treatment does lead to erythema during maintenance therapy, the dose for the next treatment will be reduced by up to 30%.

Patients with recurrence during PUVA maintenance will discontinue the study. After the end of maintenance therapy the patients will be followed up every three months in the first year after treatment, every 6 months in the second year and once a year from year 3 to 5 or until recurrence of the disease.

Arm B: control arm – Patients will receive no therapy. Patients are followed up at the same intervals like patients in study arm A (Appendix: Table 4).

Observatory patient arm:

Patients who did not response completely to therapy after a maximum of 24 weeks or 48 PUVA treatments and patients with recurrent disease (see section 7) after complete response will enter an observatory arm. Treatment of these patients will be entirely in the discretion of the treating physician. These patients will have follow-up visit at month 12 after stop of PUVA treatment or at time point of recurrence to record patient history and clinical status.

6. Definition of response

The extent of the cutaneous involvement of the disease will be determined before start of PUVA treatment and monitored during and after treatment by assessing the modified severity-weighted assessment tool (mSWAT) [STEVENS]. mSWAT is an objective, quantitative, severity-weighted method to assess the extent of CTCL lesions (Appendix: Table 3).

Quantitative tool to assess disease burden in CTCL [STEVENS]:

The body is divided into 12 regions with preassigned %TBSA based on methodology used to assess burns. The extent of skin disease is assessed for each region and quantified by using the patient's palm as a "ruler" to measure the %TBSA involvement within each region:

- Patient's palm with 4 fingers, excluding the thumb and measured from wrist to fingertips, is 1% of TBSA.
- Patient's palm without fingers is 0.5% of TBSA.

mSWAT Score calculation: Sum of %TBSA from all body regions affected by patches X severity-weighting factor of 1 + Sum of %TBSA from all body regions affected by plaques X severity-weighting factor of 2 + Sum of %TBSA from all body regions affected by tumors X severity-weighting factor of 4 (Appendix: Table 3).

Specific skin lesions will be differentiated in:

Patches: flat lesions with a diameter larger than 1 cm

Plaques: elevated/palpable lesions with increased consistency with a diameter larger than 1 cm

Tumors: nodular lesions with the longest diameter larger than 1 cm.

Response will be determined as follows:

- Complete clinical response: Complete clinical disappearance of all cutaneous MF lesions compared to baseline mSWAT. (Clinically evident postlesional erythema and/or pigmentation will not be considered as persistent disease. It will be recorded but will not affect mSWAT.) If there is clinical doubt of complete remission, a diagnostic biopsy should be performed.
- Partial response (PR): more or at least 50% reduction in mSWAT
- Stable disease (SD): less than 50 % reduction (from baseline) and less than 25 % increase of skin disease (compared with the smallest mSWAT since treatment started)
- Progressive disease (PD): more than 25 % increase in mSWAT compared with the smallest mSWAT since treatment started.

7. Definition of recurrence

Recurrence will be defined as re-occurrence of cutaneous disease, as determined by mSWAT at any time point (Complete remission = 100% clearing of skin disease (mSWAT of 0); recurrence is reappearance of skin lesions (mSWAT \geq 1)) [OLSEN (b)]: . If there is clinical doubt of continuous remission, a biopsy should be performed.

8. Adverse Events

Definitions

Adverse Event (AE)

Any untoward medical occurrence in a patient or clinical investigation subject administered a pharmaceutical product and which does not necessarily have a causal relationship with this treatment. An adverse event (AE) can therefore be any unfavourable and unintended sign (including an abnormal laboratory finding), symptom, or disease temporally associated with the use of a medicinal (investigational) product, whether or not related to the medicinal (investigational) product (see note for guidance on Clinical Safety Data Management: Definitions and Standards for Expedited Reporting).

Serious Adverse Event (SAE), Serious Adverse Drug Reaction (Serious ADR)

Any untoward medical occurrence that at any dose:

- results in death,
- is life-threatening,
- requires inpatient hospitalisation or prolongation of existing hospitalisation,
- results in persistent or significant disability/incapacity,

or

- is a congenital anomaly/birth defect

Suspected unexpected serious adverse drug reactions (SUSARs)

Suspected Unexpected Serious Adverse Drug Reactions (SUSARs) are side effects (probably or definitely connected with the administration of the investigational product), the nature or severity of which are inconsistent with the information available about the product. Information about the trial product contained in the SmPC (Summary of medicinal Product Characteristics) should be used to verify if the adverse reaction has been previously described.

Safety reporting

Investigator:

The investigator is responsible for reporting AEs, SAEs and SUSARs to the sponsor.

All serious adverse events (SAEs) should be reported immediately to the sponsor except for those SAEs that the protocol or other document (e.g. Summary of Product Characteristics) identifies as not needing immediate reporting. The immediate reports should be followed promptly by detailed, written reports.

The immediate and follow-up reports should identify subjects by unique code numbers assigned to the trial subjects rather than by the subjects' names, personal identification numbers, and/or addresses. The investigator should also comply with the applicable regulatory requirement(s) related to the reporting of unexpected serious adverse drug reactions to the regulatory authority(ies) and the ethics committee.

Adverse events and/or laboratory abnormalities identified in the protocol as critical to safety evaluations should be reported to the sponsor according to the reporting requirements and within the time periods specified by the sponsor in the protocol.

For reported deaths, the investigator should supply the sponsor and the ethics committee with any additional requested information (e.g., autopsy reports and terminal medical reports).

Sponsor:

The sponsor should keep records of all AEs reported by the investigators. These records should be forwarded upon request to the competent authority of the region where the Clinical Trial is performed.

In case of death or immediate danger of life caused by a SUSAR the competent authorities and Ethics Committee(s) concerned should be informed by the sponsor within 7 days after the event becomes known to the sponsor. Additional information should be given within further 8 days.

All other SUSAR ("requires inpatient hospitalisation or prolongation of existing hospitalisation, results in persistent or significant disability/incapacity, or is a congenital anomaly/birth defect) should be reported as soon as possible, at latest within 15 days after the event becomes known to the sponsor, to the competent authorities and Ethics Committee(s) concerned.

Information on SUSARs should be forwarded to all other investigators of the same clinical trial by the sponsor. Once yearly during the trial, a safety report and a listing of all SUSARs that occurred during the trial should be forwarded to the competent authorities and to the Ethics Committees concerned by the sponsor.

Known Side effects of PUVA-Therapy

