Appendix Figure 2: Overview of treatment effects. All patients get standard PUVA therapy. After remission patients are assigned either to controls or to nine months of maintenance therapy. The treatment effect is the extension of the median time to recurrence (black double arrow). This comes along with lower risk of recurrence (Curve (1) is higher than curve (2)). Some patients suffer from recurrence during maintenance therapy, i.e., the tilt in the straight line segment of curve (1) from month 3 to month 12. The secondary end point refers to time to recurrence after finishing treatments successfully (dashed curves (3) and (4), dashed arrow). Curve (3) gives the survival function after maintenance treatment conditional on being free from lesions after therapy. Curve (4) is a shifted version of curve (1) in order to align the survival functions for comparison.

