13.1. Study design

A randomized placebo controlled clinical trial with 3 to 6 months of PUVA therapy as control and 3 to 6 months PUVA plus 9 months of PUVA maintenance therapy as index therapy. In the Appendix Figure 1 the time-dependent probability of recurrence (“Survival function”) is given for 4 settings.

The primary endpoint of the study is the comparison of median time to recurrence after complete remission between study arm A and study arm B (comparison of curve (1) vs. curve (2), Appendix: Figure 2). A secondary endpoint is the comparison of time from end of treatment to recurrence on condition that the patient is in remission at the end of treatment comparing study arm A and B (end of treatment in study arm A, month 12 to 15; end of treatment in study arm B, month 3 to month 6). This amounts to the comparison between curve (3) and curve (4). After the accrual period patients are observed until the closing date of the study for the main statistical outcome analysis. Patients who have not experienced recurrence by the closing date are considered as censored. Treatment groups are compared by survival analysis (logrank test).

13. 2. Sample size calculations and study duration

Sample sizes were calculated with nQuery Advisor 4.0 software (www.statistical-solutions-software.com). The assumptions were $\alpha=0.05$, $\text{power}=0.8$, one(two)-sided logrank test and an accrual time of 2 years.

According to an earlier study at the dermatologic clinic the median time to recurrence after PUVA therapy was 1 year. An exponential survival function with parameter $\lambda_1=0.7$ was chosen for controls, giving a median time to recurrence of 1 year.

The alternative hypothesis (i.e. the minimum clinically relevant treatment effect) was chosen to be exponential with $\lambda_2=0.35$ (relative hazard 2, median time to recurrence 2 years) for the primary treatment effect. The overall duration of the study (to enrol 55 patients assuming an accrual period of 2 years) until closing date for the main statistical outcome analysis was assumed to be four years (accrual phase, 24 months; initial PUVA treatment of last patient enrolled, 3 months; PUVA maintenance treatment in last patient enrolled, 9 months; minimum follow-up period, 12 months). Scenario D1 and D4 refer to these assumptions. Independent of the closing date for the main statistical outcome analysis the maximum follow-up in an individual patient will be 60 months.

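### The secondary endpoint compares arm A patients still in remission after maintenance with all of arm B from randomisation, so its logrank test can show a lasting benefit that does not exist

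*Combined protocol and SAP*

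**What the plan says.** Section 3.2 lists as a secondary endpoint the "Comparison of time from end of treatment to recurrence on condition that the patient is in complete remission at the end of treatment". Section 13.1 fixes the two starting points: "end of treatment in study arm A, month 12 to 15; end of treatment in study arm B, month 3 to month 6". It names the logrank test for comparing the groups and gives no adjustment or caution for this endpoint.

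Under section 5, only patients in complete remission are randomised, at week 12, 16, 20 or 24. For arm A it adds: "Patients with recurrence during PUVA maintenance will discontinue the study". These patients pass to the observatory arm. The legend to Appendix Figure 2, printed in section 13, expects some recurrences during maintenance and describes the arm A curve for this endpoint: "Curve (3) gives the survival function after maintenance treatment conditional on being free from lesions after therapy". On the comparator it says: "Curve (4) is a shifted version of curve (1) in order to align the survival functions for comparison".

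Section 13.2 powers the endpoint in scenarios D5 to D8, changing only the length of follow-up from the primary scenarios (0.75 years shorter). D6, the counterpart of the chosen scenario D2, states 73% power with 37 per group.

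**The concern.** The condition of being in remission at the end of treatment acts on one arm only. In arm B the end of treatment is randomisation, where remission is an entry requirement, so nobody is removed. In arm A the condition removes everyone who recurs during about nine months of maintenance. One group has been filtered by its own outcome and the other has not.

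If some patients recur sooner than others by nature, arm A enters the comparison without many of its early recurrers and looks better even if maintenance does nothing. If the hazard rises with time in remission, arm A starts later on that curve and looks worse. The test cannot separate either effect from a treatment effect.

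Section 13 says maintenance is also meant to lower recurrence after it stops. This is the only planned analysis that isolates that period, so a significant result would naturally be read as proof of lasting benefit.

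**Working it through.** **Inputs from section 13.2 (D2 and D6).** One-sided 0.05; accrual R = 2 years; maximum follow-up T = 3.75 years (D2) or 3 years (D6); hazards 0.7 (control) and 0.35 (maintenance) per year; 37 per group. Maintenance lasts 0.75 years.

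**1. The plan's power for D6.** The probability of an event is 1 − [exp(−λ(T−R)) − exp(−λT)]/(λR).
- Control: 1 − (0.4966 − 0.1225)/1.4 = 0.733.
- Maintenance: 1 − (0.7047 − 0.3499)/0.7 = 0.493.
- Events: 37 × (0.733 + 0.493) = 45.4.
- Freedman power: Φ(√45.4 × (2−1)/(2+1) − 1.645) = Φ(0.60) = 72.6%, which reproduces the stated 73%.

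This calculation enters all 37 arm A patients.

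**2. Patients who actually enter.**
- Arm A at the plan's hazard: exp(−0.35 × 0.75) = 0.769, or 28.5 of 37.
- Arm A if maintenance does nothing (hazard 0.7): exp(−0.525) = 0.592, or 21.9 of 37.
- Arm B: 37 of 37.

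**3. Why selection matters.** Let risk vary between patients by a gamma frailty with mean 1 and variance v, with the control median held at 1 year. The baseline hazard is b = (2^v − 1)/v. With no effect of maintenance, the mean relative risk of those still recurrence-free at 0.75 years is 1/(1 + v × b × 0.75).
- v = 0.5: b = 0.828, giving 1/1.311 = 0.76.
- v = 1: b = 1, giving 1/1.75 = 0.57.

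Arm A would start its clock with patients at 76% or 57% of the average risk; arm B starts at 100%. With v = 0 the ratio is 1 and there is no bias.

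**4. Error rates by simulation.** 37 per arm, uniform accrual over 2 years, closing at 3.75 years, control median 1 year, 10,000 trials per case (Monte Carlo standard error at most 0.5 points). The frailty variances, fractions of long-term remitters and Weibull shape are assumptions; the documents give none. Entries are the percentage of trials significant for maintenance / for control, each one-sided at 0.05. In the last two columns maintenance halves the hazard only while it is given, so there is no lasting effect to find.

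| Recurrence model | No effect: planned test | No effect: median apparent HR | On-treatment effect only: planned test | On-treatment effect only: common landmark |
|---|---|---|---|---|
| Constant hazard | 4.8 / 5.8 | 1.01 | 4.9 / 5.7 | 5.4 / 5.3 |
| Gamma, variance 0.5 | 15.2 / 1.4 | 0.81 | 9.9 / 2.3 | 3.1 / 8.8 |
| Gamma, variance 1 | 28.0 / 0.3 | 0.69 | 16.0 / 1.2 | 1.8 / 11.4 |
| 20% long-term remitters | 21.8 / 0.7 | 0.74 | 11.6 / 2.2 | 2.1 / 11.6 |
| 30% long-term remitters | 41.2 / 0.1 | 0.60 | 18.0 / 1.0 | 1.1 / 16.8 |
| Weibull, shape 1.3 (rising) | 0.4 / 28.0 | 1.36 | 0.4 / 28.7 | 5.3 / 4.6 |

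The common landmark counts both arms from 9 months after randomisation, using only patients recurrence-free then. With no effect it favours maintenance in 4.9–5.3% of trials, and the primary test from randomisation does so in 5.0–5.3%. With 36 weeks (0.69 years) in place of 9 months, the planned test with no effect favours maintenance in 4.6, 14.7, 26.6, 20.1, 38.5 and 0.4%, in the same row order.

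**5. Power at hazards 0.7 and 0.35** (20,000 trials): D6 as set up 74.9%; the comparison as section 3.2 defines it 70.4%; the landmark 60.0%.

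**The case against.** The plan declares the condition openly, and under its own model of one constant hazard per arm the test holds its level. Every inflated rate rests on an assumed input, and a rising hazard turns the bias round. Both points are correct. They limit what can be said about size and direction, but they do not make the comparison randomised.

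The documentary evidence for patient differences is indirect. Section 1.1 says that "patients diagnosed with tumor disease or erythroderma (stages IIB-IVB) have a worse overall outcome", but this concerns survival, and of those stages only IIB is eligible. The very variable interval to recurrence is compatible with a single exponential. The best support is section 1.3.1, which reports long-term remission in an unstated share of patients. Differences are plausible but not quantified.

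A false secondary result would often sit beside a null primary. With no effect, both tests favoured maintenance in only 2.4% of simulated trials under a constant hazard and 4.4–4.9% with patient differences. However, the plan states no testing hierarchy, so a claim on the secondary endpoint alone is not barred. When maintenance works only while given, both tests were positive in 9–12%. The primary analysis also runs past maintenance and carries some information on persistence, though it does not isolate that period.

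Finally, a common landmark also conditions on post-randomisation status and is not neutral. That stands, and it is why description is the preferred remedy.

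**Conclusion.** The concern holds. The asymmetry follows directly from sections 3.2, 5 and 13.1 and needs no assumption. Its effect does need one: there is no bias if all patients share one constant hazard, nor from selection if nobody recurs during maintenance. Under the assumed patient differences, the one-sided 5% test favours maintenance in 15–41% of trials when maintenance does nothing, and in 10–18% when it works only while given. Under the assumed rising hazard it favours control in about 28%. A significant result in either direction therefore could not be read as evidence about lasting benefit. The loss of power is a lesser matter: about 70% against the stated 73%. The primary comparison from randomisation is sound. This should be corrected before analysis.

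**What to change.** Report curves (3) and (4) descriptively, with no logrank test and no claim of lasting benefit, and rest any treatment claim on the comparison of all randomised patients from randomisation.

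Reconcile which arm curve (4) shows. The Figure 2 legend derives it from curve (1), the maintenance curve, whereas section 13.1 uses (3) against (4) as arm A against arm B.

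If a post-maintenance comparison is still wanted, use one common landmark in both arms: patients recurrence-free at the visit 36 weeks after randomisation or start of maintenance (Appendix Table 4, columns +48, +52, +56 or +60, footnote o). Before that, reconcile the section 5 statement "After 9 (10, 11, or 12) months of maintenance therapy (14 treatments) patients will discontinue therapy" with the 9 months used in section 13. Label the analysis supportive. State that, if patients differ in risk, it holds its level only when maintenance has no effect at all, and that it leans against maintenance when maintenance works during treatment. Restate the secondary power: about 70% for the comparison as now defined, about 60% for the landmark.

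The cost is analysis and wording only, with no new visits or data. The descriptive option gives up a formal test of lasting benefit. The landmark has lower power and, with patient differences and an on-treatment effect only, favours maintenance in 1–3% of trials and control in 9–17%.
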